To identify a dose of pregnenolone that demonstrates bioavailability, tolerability and that is associated with a significant change in a biosignature, a one-way repeated measure multivariate analysis of variance (MANOVA) with dose as a within subject variable and exit biosignature engagement and overall tolerability (as assessed by total SAFTEE scores) as outcome measures will be performed using the MANOVA statement in the PROC GLM function in SAS 9.4.

Additionally, the results from the R61 phase will be used to determine whether the trial progress to the R33 phase. Using the results of these analyses, go/no-go rules will then be applied to determine if the study progresses to the R33 phase. The "go" criteria will be defined as meeting 2 of 3 of the biological signatures, with a medium effect size (defined as Cohen's d \geq 0.5) in the proposed direction.

Go:

At least 2 of 3 biosignatures (amygdala-PCC, dIPFC-insula, occipital GABA concentration) achieve at least a medium effect size (defined as Cohen's d ≥ 0.5) in the proposed direction (increased rsFC with fMRI, increased GABA with MRS). Biomarkers were selected based on their relevance to depression, antidepressant response and postulated pregnenolone (or active metabolite) mechanism(s) of action. A detailed justification of the biosignatures with literature references is provided in the Research Strategy (section 3.3.e.)

- If more than one biosignature achieves the proposed effect size, then the project proceeds to the R33 phase and includes any biosignatures reaching the proposed effect size. Two of three biosignatures need to be in the proposed direction. If one or two of the biosignatures is on the opposite direction of prediction, then this will result in a "no-go" signal.
- The dose (500 mg/d or 800 mg/d) with a go on biosignature must show adequate tolerability. Tolerability will be defined as no SAEs related to the study medication and no more than 10% of participants have a moderate or severe AE that is related to the product.
- If both doses of pregnenolone achieve the go threshold, including having adequate tolerability, (on either the same or different biosignature) then the dose with the largest effect size on a biosignature (defined using Cohen's d) on a biosignature will be selected for the R33 phase.

No-go:

- None of the go rules are achieved.
- A biomarker(s) achieves proposed effect size, but in the opposite direction of prediction.

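### Section 9.6 returns both Go and no-go when two biosignatures reach d ≥ 0.5 and the third falls between −0.5 and 0

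*Combined protocol and SAP*

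**What the plan says.** Section 9.4 says that the analysis at the end of R61 determines whether the trial goes on to R33, and section 9.6 supplies the rule.

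- The Go rule is stated twice: the "criteria will be defined as meeting 2 of 3 of the biological signatures, with a medium effect size", and "At least 2 of 3 biosignatures (amygdala-PCC, dIPFC-insula, occipital GABA concentration) achieve at least a medium effect size", both in the proposed direction, which is an increase for all three.
- The first bullet under Go restates it: "If more than one biosignature achieves the proposed effect size, then the project proceeds to the R33 phase".
- The same bullet adds a condition, "Two of three biosignatures need to be in the proposed direction", and closes with the sentence on opposite direction: "If one or two of the biosignatures is on the opposite direction of prediction, then this will result in a" no-go signal.
- The direction item of the No-go list reads: "A biomarker(s) achieves proposed effect size, but in the opposite direction of prediction".
- Go is assessed by dose. "The dose (500 mg/d or 800 mg/d) with a go on biosignature must show adequate tolerability", and a further bullet begins "If both doses of pregnenolone achieve the go threshold, including having adequate tolerability". Section 9.2 likewise compares each dose with placebo separately.

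**The concern.** The sentence on opposite direction sets no magnitude, so read literally an observed d of −0.01 on one biosignature vetoes the project. The 2-of-3 rule and the No-go list do not veto it. Nothing says which text governs.

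This is the decision rule for R33. If one biosignature truly does not respond, the sign of its estimate is a coin toss, and the answer then depends on which sentence is followed. If the reading is not fixed before unblinding, it can be settled after the results are known.

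**Working it through.** **Step 1: the plan's own figure.** The only stated figure nearby is power above 90% at d of about 0.82 (section 9.2). For a paired t-test, two-sided α = 0.05, noncentrality d√n:
- n = 31: 0.82 × √31 = 4.57, power 99.3%.
- n = 23 (31 × 0.75 = 23.25): 0.82 × √23 = 3.93, power 96.4%.

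The claim holds. The conflict does not depend on it.

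**Step 2: the sentences side by side**, for one dose versus placebo with tolerability met.

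| Observed d | 2-of-3 rule and proceeds sentence | Two-in-direction condition | Opposite-direction sentence | No-go list |
|---|---|---|---|---|
| 0.6, 0.6, 0.3 | Go | met | not triggered | not triggered |
| 0.6, 0.6, −0.01 | Go | met | no-go | not triggered |
| 0.6, 0.6, −0.49 | Go | met | no-go | not triggered |
| 0.6, 0.6, −0.5 | Go | met | no-go | no-go |

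Rows two and three are the conflict zone. In the last row the No-go list joins the veto, but the 2-of-3 sentences still read Go, so precedence is missing there too.

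**Step 3: how often one dose lands in the zone.** Assumptions: d is the mean paired difference over the SD of the differences; biosignatures are independent; n = 31. Observed d = t/√n, with t noncentral on n − 1 df. The true effects are scenarios: 0.82 is the plan's detectable effect, 0.5 its threshold. For true d (0.82, 0.82, 0):
- P(observed d ≥ 0.5 | true 0.82) = 0.9552.
- P(−0.5 < observed d < 0 | true 0) = 0.4954.
- Conflict zone: 0.9552² × 0.4954 = 0.452.

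P(Go) is 91.3% under the 2-of-3 rule alone, 90.9% if only d ≤ −0.5 blocks, and 45.7% if any opposite sign blocks. For (0.5, 0.5, 0) the figures are 26.1%, 26.0% and 13.2%.

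**Step 4: project level.** Either dose can carry the project, so the one-dose gap of 91.3 − 45.7 = 45.6 points overstates the effect. I simulated participant-level dose-minus-placebo differences with equal effects at both doses, tolerability met and the veto judged within each dose. The correlation between the two dose contrasts is 0.5, the value implied by a shared placebo with equal variances and equal correlations. The correlation between biosignatures was varied, because both connectivity measures come from the same resting-state scan. The documents give none of these correlations. Entries are P(Go) under the 2-of-3 rule alone versus an any-sign veto, with the gap in points.

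| True d | Biosignature correlation 0 | Biosignature correlation 0.5 |
|---|---|---|
| 0.82, 0.82, 0 | 97.9 vs 63.1%: 34.8 | 97.8 vs 65.7%: 32.1 |
| 0.5, 0.5, 0 | 40.9 vs 22.6%: 18.3 | 49.7 vs 38.5%: 11.2 |
| 0.82, 0.82, 0.2 | 98.1 vs 92.3%: 5.8 | 97.8 vs 92.9%: 4.9 |
| 0.5, 0.5, 0.2 | 44.6 vs 40.3%: 4.3 | 51.6 vs 50.4%: 1.2 |
| 0.5, 0.5, 0.5 | 70.5 vs 70.2%: 0.3 | 68.8 vs 68.8%: 0.0 |

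At biosignature correlation 0.3, the first two gaps are about 33 and 14 points. If only d ≤ −0.5 blocks, P(Go) is within about 0.2 points of the 2-of-3 rule throughout.

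Sensitivity for (0.82, 0.82, 0) with independent biosignatures:
- Dose-contrast correlation 0.2: 98.9 vs 67.8% (31.1 points).
- Dose-contrast correlation 0.8: 95.8 vs 56.7% (39.1 points).
- n = 23, dose-contrast correlation 0.5: 95.9 vs 60.8% (35.1 points).

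**The case against.** The best defence is that context supplies the missing size. The disputed sentence closes a bullet that opens with biosignatures reaching the effect size, and the No-go list restates the direction rule with that size. An any-sign veto would also leave the condition that two of three lie in the predicted direction almost without purpose. On that reading opposite means d ≤ −0.5, and results between −0.5 and 0 are Go.

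This is plausible and probably what was intended, but the sentence does not say it. Even if it did, the 2-of-3 sentences would still read Go at d ≤ −0.5 with no stated precedence.

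A second objection concerns scale. The plan predicts increases in all three biosignatures, and under that hypothesis the conflict almost never arises. That stands: the large gaps need a third true effect near zero, and the (0.5, 0.5, 0) gap shrinks as the biosignatures become correlated.

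A reader might infer two stronger points that the documents do not support.
- That every other sentence positively gives Go. The two-in-direction sentence is a necessary condition that happens to be met, and the No-go list is only not triggered. The clash is between the 2-of-3 rule, with its restatement, and one unqualified sentence.
- That an opposite result at one dose would block the other dose. No sentence says so, and the wording of sections 9.2 and 9.6 is by dose.

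**Conclusion.** Section 9.6 contradicts itself as written, and the contradiction needs no calculation to see. Its practical size does rest on assumptions: paired-difference d, n = 31, tolerability met, equal effects at both doses and a dose-contrast correlation of 0.5. On those, the reading chosen moves the chance of reaching R33 by about 32 to 35 points for true effects (0.82, 0.82, 0) and about 11 to 18 points for (0.5, 0.5, 0). It moves it by about 1 to 6 points when the third effect is 0.2, and by less than 1 point when all three are at least 0.5.

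It would be wrong to infer that the ambiguity is likely to decide this trial; that depends on whether one biosignature is truly unresponsive. It should still be corrected before unblinding, because the rule governs progression and the correction is cheap. R61 data collection, effect estimates and the primary model are unaffected.

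**What to change.** Before unblinding, reconcile the direction sentences of section 9.6 into one rule, applied to each dose versus placebo, and state that it takes precedence over the other Go sentences. The sponsor should choose one version.

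- **Version A** (matches the present No-go list and avoids a veto by noise): *A dose meets the biosignature criterion if at least two of three biosignatures have d ≥ +0.5 and none has d ≤ −0.5.*
- **Version B** (only if an any-sign veto is intended): the same rule, ending *and none is below 0*. The sentence requiring only two of three in the predicted direction is then deleted.

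In either version, add two statements:
- The direction rule is judged within each dose.
- R33 carries forward the biosignatures with d ≥ +0.5 at the selected dose. The present text allows the doses to pass on different biosignatures and does not say which dose decides.

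The tolerability and dose-selection text stays as it is. The cost is a few sentences, with no extra data or participants.

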10. DATA COLLECTION AND QUALITY ASSURANCE

10.1 Data Collection Forms

Data will be collected from each participant by the lead research coordinator. If the lead research coordinator is unavailable, the back-up research coordinator will complete the participant's study visit. All data collection and study visits will be held in BL8.224 (Psychoneuroendocrine Research Program Office at UT Southwestern). All the neuroimaging data collection will take place at AIRC.

When available, NCCIH templates (part of Clinical Research Toolbox) will be used to aid in data collection. These include the adverse events form, demographics form, documentation of informed consent, inclusion/exclusion criteria, medical history, physical exam, prior and concomitant medications, randomization and enrollment, serious adverse events form, study completion, and vital signs. The psychiatric evaluation and clinician follow-up will be performed by a PI or a study clinician and completed on forms created by the office staff to include specific data requirements for this study. Blood panel results will be received from Quest Diagnostics, Inc. via fax, signed and dated by a study clinician, and kept in the participant's binder. ECG results will be printed immediately, reviewed and signed by a study clinician, and added to the participant's binder as well.

The majority of study assessments will be given on standardized and validated paper forms or, where possible, entered directly into REDCap data collection system.

This includes the SCID-CV, HRSD, C-SSRS, SAFTEE, and UCLA loneliness scale. SCID-CV, HRSD, and C-SSRS are observer-rated and SAFTEE and UCLA is a self-report document.

Blood samples for routine labs (CMP and CBC) will be sent to Quest Diagnostics, Inc. for analysis. The blood for neurosteroid assays will be aliquoted into a 2mL cryovial and stored at McDermott Center for Human Growth and Development until the samples are ready to be shipped to [name] at Duke University. All blood samples will be labeled with a 4-digit unique identifier assigned to each participant. Quest Diagnostics also requires specific information to be provided in order to aid in sample processing. This information will include year of birth (but not date and month) and participant sex in addition to the 4-digit identifier.

Neuroimaging data will be stored on UT Southwestern servers as part of the standard AIRC protocol until the data are ready for analysis by the labs of [name] and [name].

All study documents will be kept in secure locations. Participant binders are double-locked will be kept in locked file cabinets behind locked office doors at all times. Electronic forms will be kept on password encrypted files that are backed-up to secure, encrypted, off-site servers maintained by UT Southwestern Medical Center.

10.2 Data Management

REDCap – a self-managed, secure, web-based solution that is designed to support data collection strategies for research studies – will be used in this study. This tool provides functionality and features enabling researchers to rapidly develop databases for collecting and managing research data. All data entered in REDCap will have an associated case report form kept in a participant's binder. The REDCap system will be set up by the study personnel at UT Southwestern, and will be validated by the UT Southwestern biostatistician ([name], B.S.).

Data will be transcribed from source documentation into REDCap, and will be limited to questionnaire data (i.e., no protected health information). The transcribed data will be consistent with the source documents or the discrepancies will be explained in a note-to-file. All entries, corrections, and alterations will be made by the investigator or other authorized study personnel. The REDCap system maintains a full audit trail of data entry, data corrections, and data queries. Participant binders will be double-locked, and any electronic study logs will be kept in password-protected files that are backed-up to secure, encrypted, off-site servers maintained by UT Southwestern Medical Center.

The PNE Office at UT Southwestern Medical Center will be in charge of the majority of data collection and management. All study procedures, with the exception of the MRI scan, will occur at the PNE Office in private offices and exam rooms. ECGs for these visits will be performed at the P-CRI office of UT Southwestern Medical Center (BL6). The research coordinator will collect data and perform data entry for these visits.

Once the study visit has been completed, all assessments will be scored. The lead research coordinator will input each participant's data into their specific chart. Per PNE Program guidelines, the research coordinator must have scored and entered data for a study visit within, ideally, 2 business days of completion of said study visit.

Once data have been entered, the back-up research coordinator will validate the lead research coordinator's data. Chart validation consists of the back-up research

coordinator scoring the data again to ensure that the lead research coordinator's calculations and entry are accurate. Per PNE Program guidelines, chart validation must be completed within, ideally, 7 days of initial data entry (9 days after study visit), including resolution of any errors or discrepancies.

Participants will be identified in REDCap via a unique 4-digit participant ID assigned to all randomized participants at Baseline visit. No personal identifiers will be used in any publication or communication used to support this research study. The subject number will be used if it becomes necessary to identify data specific to a single subject. Personal identifiers will be removed from photocopied or electronic medical and research records.

10.3 Quality Assurance

10.3.1 Training

Staff members are already familiar with the assessments from prior or ongoing research projects. However, additional refresher training will be set up if needed on SCID-CV, HRSD, and C-SSRS and conducted by [name] (Departmental Trainer).

Furthermore, a mock patient interview will be conducted using the HRSD to establish inter-rater reliability, and the intraclass correlation coefficients (ICC) will be calculated. Additional training will be provided, when needed, for individual raters with scores outside the acceptable range. The goal will be an ICC of at least 0.8. Inter-rater reliability training will be completed every 6 months.

In addition, staff members have completed training requirements for Human Subjects Protection, HIPAA and Good Clinical Practice. These courses have to be completed every 3 years as per UT Southwestern IRB policy.

The research coordinators associated with this study have been phlebotomy certified as a Certified Venous Access Specialist (CVAS) through Becksford Health Services, LLC. Renewals of phlebotomy certification will be obtained through Becksford Health annually.

10.3.2 Quality Control Committee

The PNE Quality Control Committee oversees all training and data maintenance to ensure the highest quality data is obtained across all study procedures. To do this, the Committee will perform regular reviews of study participant charts and electronic databases, as well as perform regular chart audits. Chart validation will be monitored via checklists that show the progress of chart completion. The committee will also ensure that all study staff remain updated on their trainings and certifications (e.g. CVAS phlebotomy, HIPAA, Conflict of Interest) in conjunction with the training committee.

10.3.3 Metrics

Inter-rater reliability on mood assessments will be measured using a mock patient interview that will be administered by the research coordinators. Scores will be compared using an ICC. The PNE Program standard is to achieve an ICC ≥ 0.8 on all mood assessments. Any mood assessment that results in an ICC below the goal will require an additional training to resolve any administration discrepancies.

10.3.4 Protocol Deviations

Protocol deviations will be avoided if possible. However, should deviations occur, they will be captured as they occur. Major protocol deviations will be documented using the online IRB Protocol Deviation Form and reviewed by the research coordinator and the PI. Major deviations will be reported to both NCCIH and the UT Southwestern IRB within 5 business days of the PI becoming aware of the deviations. Minor deviations will be summarized and reported to the UT Southwestern IRB at the annual continuing review.

10.3.5 Monitoring

Internal monitoring will occur on an ongoing basis and at least quarterly via chart audits, and will be supervised by the PI. NCCIH will also perform site monitoring visits. All materials and resources will be made available to NCCIH site monitors to provide a fully encompassing review of site performance and protocol compliance.

11. PARTICIPANT RIGHTS AND CONFIDENTIALITY

11.1 Institutional Review Board (IRB) Review

This protocol and the informed consent document (to be attached once final and approved) and any subsequent modifications will be reviewed and approved by the UT Southwestern IRB in accordance with the Federal Wide Assurance (FWA) on file with the Department of Health and Human Services.

11.2 Informed Consent Forms

A UT Southwestern IRB-approved written signed informed consent form will be obtained from each participant after full disclosure to the participant. Full disclosure means that the participant has been given sufficient information and time to understand the nature of the research project and risks that may be associated with the treatment. The consent form will describe the purpose of the study, the procedures to be followed, and the risks and benefits of participation. A copy will be given to each participant, and this fact will be documented in the participant's record. The research coordinator, with PI delegation, will obtain the informed consent and answer any questions about the study. The PI will always be available to answer any additional questions and provide more information about the study.

This research study will exclude vulnerable populations including pregnant or nursing women, the incarcerated, and people with severe cognitive disorders. Because many of the assessment tools have not been validated in other languages, non-English speaking individuals will be excluded. Participants with language limitations will be accommodated if the adaptations allow for clear understanding and completion of the assessments. The locations of the research study are all handicapped accessible. Children under the age of 18 and adults over the age of 65 are excluded from the study.

The consent forms are reviewed annually by the UT Southwestern IRB.

11.3 Participant Confidentiality

The research site follows the policies and procedures for maintaining participant confidentiality according to HIPAA. The participant records from the research study and the executed consent forms will be maintained in locked file cabinets in one of the PI's offices on campus. All data will either be maintained in locked file cabinets or in computers with password-protected access. Information will not be released without written permission of the participant, except as necessary for monitoring by IRB, DSMB, the FDA, the NCCIH, and the OHRP. Any data, specimens, forms, reports, and other records that leave the site will be de-identified by a participant identification number (PID) to maintain confidentiality.

Any email communication using identifiable participant information will utilize the UT Southwestern encryption system. During the consent process, all participants will be given the Notice of Privacy Practices (NPP) brochure that outlines the rights and responsibilities of UT Southwestern (hospitals, healthcare providers, research laboratories, and pharmacies) and the participant when dealing with the provision of protected health information related to care received and participation in research. After presenting the participant with the brochure, the staff members will collect a signature from the participant acknowledging receipt of the NPP brochure.

11.4 Study Discontinuation

The study may be discontinued at any time by the IRB, the NCCIH, the OHRP, the FDA, or other government agencies as part of their duties to ensure that research participants are protected.

12. COMMITTEES

Quality Control Committee: [name] (chair).

The goal of the committee is to ensure that the highest quality of data is being obtained, collected, entered, and reported for all clinical studies. In addition, the chair ensures staff members understand and follow current protocol and updated consent forms. She also maintains and oversees data entry and validation. The quality control committee will audit reliability of assessment administration, chart validation, back-up training, protocol and consent form continuity.

Training Committee: [name] (chair)

The committee chair will assist with overseeing the training process for new PNE employees, interns and medical students. The chair will ensure that all training requirements are met by newly hired PNE employees, as well as current staff members. The chair will also schedule inter-rater reliability testing for the group every 6 months.

